5.3 Specimen management and storage

As the transmission of HIV and other blood-borne pathogens can occur through contact with contaminated needles, blood, and blood products, appropriate blood and secretion precautions will be employed by all personnel in the drawing of blood and handling of all specimens for this study, as currently recommended by the Centers for Disease Control and Prevention. All infectious specimens will be transported using packaging mandated in the Code of Federal Regulations, 42 CFR Part 72. Specimens, inclusive of the cervical or vaginal biopsies that are not used immediately will be processed and stored at CDC for future testing. Plasma and peripheral blood mononuclear cells (PBMC) will be stored at -70°C. Vaginal swabs, Anal swab and CVL supernatants will be stored at -70°C. Specimens collected will be used for the evaluations described within this protocol. Any remaining specimens will be stored for potential future use only if the patient has consented to storage of specimens. These specimens may be used in the future to further evaluate HIV, immunologic microbiologic factors of interest or as a source of DNA for future genetic analysis. A subject may request that any stored specimens are destroyed prior to completion of the study. Specimens will be stored with the study ID of participant only, and no patient identifiable information. At study completion any identifiers that link the subject to the study ID will be destroyed. Specimen storage will be for an indefinite amount of time if consent for storage had been signed. During the consent process, specimen storage will be discussed and participants will be consented to allow for storage and future testing of specimens.

5.4 Specimen collection considerations

Swabs and cervicovaginal lavage collections are minimal risk procedures. Specimens contaminated with blood may need to be excluded from our analyses. Every effort will be taken to reduce such risks by starting with the least invasive collections (swabs and tear-flo strips), then proceed with cervicovaginal lavage collection which introduces specimen dilution. We do not anticipate that collecting multiple samples in this order will influence any of the subsequent data collection endpoints, given the large vaginal surface. By maintaining a consistent order of specimens collected at each visit we will minimize experimental variability.

6 Ethics and Risks

The study will not commence until the study protocol has been reviewed and approved by the Emory University institutional review board (IRB) and the Grady Health System Research Oversight Committee.

6.1 Potential risks

The risks involved in study participation are those related to providing personal information about sensitive topics such as sex, contraception, antiretroviral medication use, and pregnancy. Participants' privacy and the confidentiality of data will be protected through training of interviewers and other study staff, conducting all interviewing and physical examinations in private, storing study materials in a locked room, and securing computer files that include identifiers. Only the study identification number will identify participant research records. Linkages between the ID number and participants' identifying information will be maintained in a computer database that is password protected and only accessible to study staff. These linkages will be destroyed after completion of study activities. Breaches of confidentiality are possible, though safeguards are in place to

protect the confidentiality of participants. Thus, the potential for experiencing an adverse event is minimal.

There is a risk that the participant may get pregnant while enrolled in the study. This risk is the greatest during the first few weeks of the study before the participant starts their contraceptive. To reduce this risk we will ask the participant to either abstain from sex or use condoms during this time. If pregnancy occurs during the study, we will refer the patient for further care.

Each of the four study visits consists of a brief interview, blood collection, pelvic examination, and vaginal sample (swab and lavage) collection. The potential additional risks to participating include discomfort from the blood draw and gynecologic exam with specimen collections, as outlined below:

1. The standard risks of phlebotomy: Skin irritation at the collection site, some bleeding, bruising, fainting, and pain are risks associated with blood collection. There is also a very small risk of infection at the collection site.
2. Discomfort from physical and gynecologic examination: Gynecologic examinations may cause both physical and emotional discomfort.
3. The risks associated with suspicion of a STI or vaginitis: Individuals who test positive or have any suspicious examination finds concerning for any infections during the research evaluation, will be referred for clinical evaluation and/or treatment. Individuals diagnosed with an STI may experience emotional discomfort upon receiving their diagnosis or upon notifying sexual partners, which would be recommended by their provider during

counseling if a test result is positive.

4. Risks associated with their selected contraceptive – including routine risks during insertion and side effects.

Risks associated with cervical or vaginal biopsy collection is bleeding and infection. Subjects will be informed on how to care for the area and to contact the PI or their medical care provider if there is a persistent smell, bleeding or discomfort. These procedures are not anticipated to be associated with any deleterious impact on participants' health or well-being.

6.2 Protection against risks

In implementing this protocol, we will be following HHS guidelines for research practices outlined on 45 CFR 46 (also known as the common rule). The investigators will adhere to the basic principles of "Good Clinical Practice" as outlined in Code of Federal Regulations (CFR) 312, subpart D, "Responsibilities of Sponsors and Investigators," CFR 21, part 50, and CFR 21, part 56 and Section 4 of International Conference on Harmonisation of Technical Requirements for Registration of Pharmaceuticals for Human Use (ICH) Harmonized Tripartite Guideline for Good Clinical Practice. Specifically, we will provide careful training of study personnel who interview or collect participant samples. Training will include a component on careful patient counseling to enable the counselor to recognize complications, and when indicated, provide immediate referral for evaluation. A study participant will be informed of the voluntary nature of this study and that they may elect to not answer certain questions or to discontinue participation in the study at any time. Additionally, comprehension of study procedures will be assessed by study staff prior to

signing the informed consent form. Study staff will first review the informed consent document.

After reviewing the consent document, the research staff member will ask the participant the appropriate comprehension questions (see Appendix B). If a participant incorrectly responds to one of the comprehension questions, the staff member will further clarify study procedures.

Those participants who incorrectly respond on a second attempt, will be ineligible to participate in the study. Risks from receiving the contraceptive will be minimized by ensuring that a qualified trained clinician performs all insertions and a comprehensive consent for that contraceptive is reviewed prior to their receipt of the contraceptive as part of routine clinical practice at the clinic.

All laboratory specimens, evaluation forms, reports, and other records that leave the site to collaborating laboratories will be identified by a coded number only, to maintain subject confidentiality. All study records will be kept in a locked cabinet or on password-protected computers that will be stored in locked cabinets, accessible only to Emory based study research staff. The clinical data associated with the pelvic examination and placement of the contraception that would correspond to routine clinical care data will be shared with the patients clinical care provider, and included in their Grady electronic medical record,. This information in the electronic medical record is available to all members of the participant's clinical care team. We will encourage patients to share their results with any health care providers they have outside of the Emory or Grady setting, if they wish; however we will not attempt to contact these providers directly. For sexually transmitted diseases that are identified, a clinician on the research team will contact the individual directly via phone to discuss results and clinical referral. As study samples will be processed in a research lab, these results can not independently be acted on for clinical

management, thus patients will be referred for clinical care. For any positive results identified during their research visit, such as a positive pregnancy test or vaginitis, a clinician from the research team will be available to counsel the patient at that visit on their results and discuss referral for care.

Any other clinical information will not be released without written permission of the subject, except as necessary for monitoring by IRBs at participating institutions or the Office for Human Research Protection. The study may be discontinued at any time by an IRB at a participating institution or the Office for Human Research Protection.

6.3 Benefits to participation

The benefits of this research extend to potentially leading to improvements in the reproductive health care provided at the facility. Moreover, the results could potentially impact individuals globally as we aim to better understand transmission of infections such as HIV, which can improve or better target our methods of prevention. Participants will receive a \$50 compensation for each study visit, including their screening visit with a maximum of \$250 received if she completes all study activities.

6.4 Importance of the knowledge gained

The current study could help us to better understand the biologic effects of hormonal contraception on HIV transmission risk. If hormonal contraception increases the risk of transmission, dual protection methods with non-hormonal methods, such as the copper IUD and condoms, may be an important alternative strategy. The knowledge gained from this research may be used on multiple levels to help prevent unintended pregnancy, HIV transmission, and STI

infection.. Study findings will be disseminated further via abstracts submitted to scientific meetings and manuscripts submitted to peer-reviewed journals.

6.5 Limitations and Future Directions

By design the study does not directly address the risk of HIV acquisition from hormonal contraceptives; rather, it explores surrogates that might provide a mechanistic explanation to this purported impact of contraceptive hormone use. Being exploratory in nature, the sample size is small, and we may not be able to detect small differences in some of the outcomes. We have carefully selected our markers to focus on our study aims, however we acknowledge that additional markers may be of interest and can be explored in future evaluations. Additionally, the design is limited by all the inherent biases and confounding associated with a non-randomized, non-blinded study design. Attempts to control for covariates will be performed in the analysis. Further, as our follow-up is limited to 3 months, we cannot evaluate the impact of long-term contraceptive use nor the effect of irregular bleeding on HIV risk. Furthermore, we acknowledge that many other factors that influence HIV susceptibility warrant further investigation, such as epithelial integrity and endogenous microbicides. We plan to use these banked samples to explore some of these other potential mechanisms in future research. The data generated from the successful completion of this study will be instrumental in the design of a future prospective contraceptive trial to explore HIV acquisition risk and to establish safe family planning options for high-risk women.

6.6 Inclusion of women, minorities, and children

Pursuant to HHS policy, women (females over the age of 21), members of minority groups, and children should be included in biomedical and behavioral clinical research projects involving human subjects. The proposed study conforms to this policy.

7 Monitoring and Oversight

7.1 Site monitoring

Site monitoring may be performed by the Emory University's IRB and Office of Research Compliance, OHRP, FDA, or other government regulatory authorities. Clinical research site monitoring may include the review of the individual participant records, including consent forms, CRFs, supporting data, laboratory specimen records, and medical records (physicians' progress notes, nurses' notes, individuals' hospital charts) to ensure protection of study participants, compliance with the protocol, and accuracy and completeness of records. The monitors may also inspect sites' regulatory files to ensure that regulatory requirements are being followed. The investigator will make study documents (e.g., consent forms, CRFs) and pertinent hospital or clinic records readily available for inspection.

7.2 Data quality assurance and protection

There will be study protocol and procedure training for all study personnel prior to beginning of the study. A standard operations manual will be available to staff to refer to for operational details in running the study.

Each woman screened will be assigned a participant identification number (PIN) at the time of study entry. The PIN will be used on all data forms, specimens and communications related to the study.

Samples will be labeled at the time of collection and processing using study labels. Clinical research forms (CRFs) will be used to collect all study related data, including demographic, clinical, and laboratory data at study entry, and additional clinical data at subsequent study visits. Subjects will be identified only by the PIN on the CRFs. To maintain subject confidentiality, only a coded number will identify all stored laboratory specimens, forms, reports and other records. All records will be kept in locked file cabinets, accessible only by local study staff. Electronic files will be password-protected, with access only by authorized study personnel. Clinical information will not be released without written permission of the subject, except as necessary for monitoring from funding agencies and designees or except as mandated by law.

The study investigators will provide instructions concerning the recording of study data on CRFs. It will be the responsibility of the study investigator to assure the quality of computerized data. This role extends from protocol development to generation of the final study databases. Data from screening forms and study visit will be entered into Microsoft Access 2007. Electronic data will be secured in a password protected database that is accessible to members of the Emory investigative team. The Emory study investigators will maintain the link in a separate file that associates subjects with their PIN.

Staff will double-enter data using appropriate software. The data entry screens will be prepared with built-in quality control checks. To safeguard against loss of data, backups of the data will be made. Study staff will train the data entry staff in all data management procedures. We will conduct all statistical analyses using the SPSS System for Windows version 18.0, SAS Proc Mixed (version 9) or similar analysis software program. The database and the laboratory data

generated by this study will be maintained at Emory and will be accessible to collaborators. The principal investigators will be responsible for documentation of these data.

The initial data entry and maintenance of laboratory data, identified only by PIN, generated will be the responsibility of the laboratory investigator generating and entering the data and of study investigators who will oversee data quality.

7.3 Protocol violation

A protocol violation is any intentional or unintentional change from the IRB-approved protocol that adversely affects (1) the risk/benefit ratio of the study, (2) the rights, safety, or welfare of the participants or others, or (3) the integrity of the study. Examples include breach of confidentiality, inclusion of ineligible participants, or initiation of study procedures before participant has signed the consent form. If a protocol violation were to occur, it would be documented on the appropriate protocol deviation report form, and if the violation were to meet reporting requirements, it would promptly be reported to the participating IRBs.

7.4 Adverse events

An adverse event (AE) is defined as any health-related reaction, effect, toxicity or abnormal laboratory result that a study participant experiences during the course of the study, irrespective of relationship to the study intervention. This includes changes in a participant's condition or laboratory results that have or could have a deleterious effect on a participant's health or well-being. A serious adverse event (SAE) is defined as any experience that is fatal or life-threatening, requires in-patient hospitalization or prolongation of an existing hospitalization, or results in a persistent or significant disability or incapacity.

This study includes interviews, blood draws, pelvic examinations, and vaginal sample (swab and lavage) collections. These activities are not anticipated to be associated with any deleterious impact on participants' health or well-being. AEs will be managed according to good clinical practice and the judgment of the on-site physician. All clinical and laboratory AEs will be followed-up closely by study staff. Any SAEs will be expeditiously reported to the principal investigators, via a designated SAE form. Notification and submission of SAE forms should occur within 48 hours of the site awareness of the SAE. The PI will then make the final independent judgment as to the severity, relatedness, and anticipated or unanticipated nature of the SAE and finalize the Human Subjects Adverse Event Report Form. If the event is determined to be serious, unanticipated, and the relationship is anything other than probably or definitely not related, then the PI will report the event within 48 hours and submit the required forms to the IRB at Emory and Grady will be simultaneously notified. Thus, all anticipated SAEs that are at least possibly related to study intervention and all deaths that are at least possibly related to study intervention will be submitted to Emory IRB, and Grady ROC.

8 Statistical Considerations and Analysis

Sample Size/Statistical Considerations: We used the preliminary data from CVL of healthy women (unpublished) for our power analysis (CCR5: n=17, mean = 17.6%, Standard deviation (SD) = 17.4%, CD38 n=6, mean =41.9%, SD=11%), using the SD from the cross sectional data as an estimate for the SD for change. Due to the expected correlation between repeated-measures, this is a conservative estimate as the standard deviation for change should be smaller than the observed between-subject standard deviation. For evaluating change following exposure to any

contraceptive method (compared to no method), a sample size of 90 women achieves statistical power exceeding 95% to detect a **CCR5** increase of 10% (or larger) (two-sided one-sample t-test on change, 5% α -level). Similarly, with a sample size of 90 women, we achieve statistical power exceeding 95% to detect an increase in **CD38** of 10% (or larger) from before to after any contraceptive exposure. Comparing the different contraceptives, assuming an increase of 25% in **CCR5** in the DMPA group and an increase of 10% in Nexplanon group and Mirena IUD group (pre to post exposure), a sample size of 30 women per contraceptive group (Nexplanon vs. DMPA or Mirena IUD vs. DMPA) will achieve 90% statistical power to detect a contraceptive group difference of 15% (2-sided two-sample t-test on change, 5% α -level). Similarly, assuming an increase of 20% in **CD38** expressing T-cells in the DMPA group and an increase on average of 10% in Nexplanon group and Mirena IUD group, a sample size of 30 women per contraceptive group will achieve 93% statistical power to detect a contraceptive group difference of 10%.

Data Management and Statistical Analysis: Study data will be recorded on case report forms and entered into a web-based password-protected relational database (REDCap). Repeated-measures analyses using mixed linear models will be performed with the assistance of Emory CFAR biostatistical core for study endpoints and analyzed with SAS Proc Mixed (version 9) providing separate estimates of the means by contraceptive method and time on study before (weeks 1 and 3) and after (15 and 17 weeks) contraceptive administration. An unstructured variance-covariance form among the repeated measurements will be assumed for each outcome and estimates of the standard errors of parameters will be used to perform statistical tests and construct 95% confidence intervals. The model-based means are unbiased with unbalanced and missing data,

assuming missing data are non-informative and random. Mean changes over time for each contraceptive method will be tested for linear trend. Data will be summarized using adjusted means and observed differences plus 95% confidence intervals. Statistical tests will be 2-sided. A P value ≤ 0.05 will be considered statistically significant.

For multivariable repeated-measures analyses, a mixed linear model will be fit including age, body mass index, race and parity as potential baseline confounders in addition to contraceptive method, time on study and the interaction between time on study and contraceptive method. The multivariable results will be summarized with adjusted means and 95% confidence intervals. The adjusted mean for each contraceptive subgroup (DMPA, Nexplanon, copper IUD and Mirena IUD) will be defined as the mean response obtained by fitting the statistical model at the mean age and the mean BMI of the three subgroups and averaged across levels of the other risk factors. To integrate time-dependent variables, such as BV and PSA, into the longitudinal analyses, each participant at each of the 4 scheduled visits will be classified as positive or negative for each variable. Outcome change will be compared between incident cases and the other women (baseline positive and those that remain negative) after adjusting for the other covariates.

9 Dissemination of Results

The results will be disseminated in the form of abstracts submitted to scientific meetings and manuscripts submitted to peer-reviewed journals.

REFERENCES

1. UNAIDS. UNAIDS Report on the global AIDS epidemic. 2010.

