3.0 Study Objectives and Hypotheses

3.1 Research hypotheses and objectives

This research will evaluate the impact of one non-hormonal IUD and 3 different progestin-only contraceptive methods: 1) DMPA, 2) an Etonogestrel implant (Nexplanon), 3) the Levonorgestrel Intrauterine Device (Mirena IUD), and 4) Copper IUD, on known factors in the FGT that can modify HIV acquisition risk, including changes in the distribution and activation of HIV susceptible T-cells and mucosal chemokines and cytokines. One hundred and twenty (120) HIV-negative women seeking family planning will be recruited into a prospective study evaluating vaginal mucosal immunologic markers of HIV susceptibility before and after contraceptive initiation.

It is unclear how different progestin analogues and varying systemic and FGT hormonal concentrations associated with their different contraceptive delivery and pharmacokinetics may influence FGT immune function. Because many of the anticipated mucosal immune changes with

progestin-only contraceptives are mediated via estrogen suppression, we hypothesize that the impact of Nexplanon and Mirena IUD (milder anti-estrogen effect) will be significantly less pronounced compared with that of DMPA – a finding that would have significant clinical implications for family planning for women at risk for HIV.

Aim 1: To evaluate the effects of DMPA, Nexplanon and two IUDs (Mirena and copper) on the exposure on the frequency of HIV target immune cells within the female genital mucosa of HIV negative women.

Hypothesis: Compared to a no contraception baseline, there will be an increase in HIV target CD4+ T cells in the female genital mucosa following initiation of hormonal contraception and these effects will be greater with DMPA because of its more pronounced anti-estrogen action relative to Nexplanon and Mirena IUD.

Aim 2: To evaluate the effects of DMPA, Nexplanon and two IUDs (Mirena and copper) on the exposure on markers of T cell activation and trafficking in the female genital mucosa of HIV negative women desiring hormonal contraception.

Hypothesis: Compared to a no contraception baseline, there will be an increase in T cell activation and trafficking following hormonal contraception and these effects will be greater with DMPA because of its more pronounced anti-estrogen action relative to Nexplanon and Mirena IUD.

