4.1.1. Recruitment: Participants will be recruited from one of two potential sources

1) The Grady Family Planning Clinic within Grady Memorial Hospital: This site is where over 4600 healthy reproductive-aged women from across the state of Georgia seek family planning annually. Additionally, recruitment will take place at Emory Clinic Gynecology and Obstetrics practice and at the IDP/Ponce Clinic. Women who present for a family planning visit and who are interested in one of the 4 contraceptives under study will be approached for participation by study staff not involved with the individual's clinical care. Clinicians will alert the research staff of potential participants and the research staff will approach the potential participant. Research staff will read a standard recruitment script (Appendix A).

If interested, staff will complete a screening checklist to see if the individual is eligible for participation (Appendix A)

2) By self-referral: Individuals will contact study staff in response to a flyer. Flyers will be placed throughout the Atlanta community including but not limited to Grady Memorial hospital gynecology clinic, Emory Campus and Clinics. Women who contact study staff will complete a screening checklist to see if the individual is eligible for participation (Appendix A), and if interested they may be scheduled for a screening visit

Recruitment will continue until 30 individuals are enrolled into each contraceptive arm (120 total). We anticipate recruiting at the rate of ~30 participants per year and should complete accrual by year 3, all study visits should be completed by year 4. Although a randomized controlled study design ensures balance between arms, for feasibility reasons and because contraceptive choice in our population is a personal decision, the specific contraceptive type will be left to the preference of participants.

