4.2 Study visits

A brief questionnaire to assess sexual behavior and bleeding or vaginal symptoms will be asked, urine will be collected for a pregnancy test, a pelvic exam will be performed with measurement of vaginal pH using a PH meter, a swab will be collected for a wet-mount, a swab for multiplex PCR of vaginal fluid, a swab for vaginal microbiome, a CVL collection (for immunological testing and prostatic specific antigen (PSA)), a swab for gut microbiome, and blood (for immunological testing and hormonal concentrations). At visit 1, additional blood will be collected for HSV serology, HIV and RPR. At visit 2 and visit 4, a cervical or vaginal biopsy will be performed for a subset of participants that consent (10 per contraceptive arm) so that one or more samples of tissue from the cervix or vagina are acquired for evaluating HIV susceptibility and inflammation markers. At visits 1-4, two [endocervical cytobrush samples](#) of genital specimens will be collected for immune phenotyping.

Hormonal contraceptives Participants will be given the option to choose between DMPA, Nexplanon, copper IUD and Mirena IUD. DMPA will be dispensed from the Grady Pharmacy Service and will be administered every 12 weeks at the standard dose of 150 mg IM, beginning from week 3 of study enrollment and repeated at week 15. A standard Nexplanon rod Implant or the IUD (Mirena or copper) will be placed at study week 3 by [name] or a trained clinician.

The cost of study contraceptives will be covered by this study.

Of note, study visits are scheduled to ensure that the collection of pre-contraceptive samples occur at both the luteal (week 1 visit) and the follicular (week 3 visit) phases of the menstrual cycle. Serum hormone levels will confirm cycle phase. Post-contraceptive samplings are strategically delayed to avoid sampling during the initial (first 3 months) phase when irregular bleeding associated use may occur. Furthermore, the proposed sampling schedule will allow us to capture data at the trough (week 15) and peak (week 17) of the concentration-time-curve for DMPA. If bleeding at the time of a scheduled visit, the visit will be postponed to occur within one week or at a subsequent point corresponding to their intended cycle phase (luteal/follicular) or drug exposure (DMPA peak or trough) of the missed visit. Because the study requires intensive and invasive sample collection, concerted efforts will be made to *enhance retention and study completion.*

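### The multivariable model as listed has no covariate-by-time term, so age, BMI, race and parity do not adjust the between-method difference in pre-to-post change

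*Combined protocol and SAP*

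**What the plan says.** Section 8 (Data Management and Statistical Analysis) specifies repeated-measures mixed models with an unstructured covariance over two pre-contraceptive visits (weeks 1 and 3) and two post-contraceptive visits (weeks 15 and 17). For the multivariable version, "a mixed linear model will be fit including age, body mass index, race and parity as potential baseline confounders in addition to contraceptive method", followed by "time on study and the interaction between time on study and contraceptive method". That is the only interaction named. On reporting: "The multivariable results will be summarized with adjusted means and 95% confidence intervals".

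The between-method question is about change. Section 3.1 expects a rise from a no-contraception baseline, and says "these effects will be greater with DMPA because of its more pronounced anti-estrogen action relative to Nexplanon and Mirena IUD". The between-method power calculation in section 8 is likewise a "2-sided two-sample t-test on change", with 30 women per group.

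Allocation is not randomised. Section 4.1.1 states that "the specific contraceptive type will be left to the preference of participants". Section 6.5 acknowledges the resulting confounding, and its answer is: "Attempts to control for covariates will be performed in the analysis".

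**The concern.** Age, BMI, race and parity enter as main effects only. A main effect moves a woman's whole profile up or down and does not alter its shape over time. The model therefore adjusts the method means at each visit but not the difference between methods in how far those means move, which is the quantity the aims compare.

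Much confounding is already dealt with, because each woman is her own control and anything that shifts all her visits equally cancels. What remains is a covariate that differs between self-chosen methods and also predicts how much the marker changes. Among these four covariates, that is the only kind of confounding that can bias a difference in change, and the listed model leaves it in place.

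There is also a risk in interpretation. The multivariable and unadjusted results for this contrast would agree exactly with complete data, and closely otherwise. A reader could take that agreement as evidence that the four covariates do not confound, when it follows from the form of the model.

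**Working it through.** **Inputs from section 8.** SD 17.4 points for CCR5 and 11 for CD38, used there as the SD of change; 30 women per method; planning differences of 15 and 10 points; two-sided 5% level.

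**The plan's own figures.** SE of a two-method difference = SD × √(2/30).
- CCR5: 17.4 × 0.2582 = 4.49. Noncentrality 15/4.49 = 3.34 on 58 df; power 90.7% (plan: 90%).
- CD38: 11 × 0.2582 = 2.84. Noncentrality 10/2.84 = 3.52; power 93.3% (plan: 93%).

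Both reproduce.

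**Why the main effects drop out.** Write the listed model for woman i, method g, visit j as Y = μ(g,j) + βX(i) + e(i,j).
1. Her change C(i) is the mean of weeks 15 and 17 minus the mean of weeks 1 and 3. The term βX(i) appears in both means and cancels.
2. This survives the unstructured covariance S. For any contrast c over visits (weights summing to zero), the covariance of c′Y with 1′S⁻¹Y is c′SS⁻¹1 = c′1 = 0. The only combination of visits that carries information on β is therefore uncorrelated with the change contrasts.
3. With complete data, the fitted method-by-time contrast is therefore the raw difference in mean change, with or without the covariates.

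**What is left.** If the change itself depends on X with slope γ, and the mean of X differs by δ between two methods, the bias in the difference in change is γ × δ.

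**Simulation 1.** Assumptions: four methods × 30 women, four visits, SD 17.4 per visit, within-woman correlation 0.5, one covariate 0.5 SD higher with DMPA, true difference zero, maximum likelihood with unstructured covariance.

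| Setting | Unadjusted | Model as listed | Covariate × period |
|---|---|---|---|
| Slope on change 5 per SD, level effect 5; complete data; 600 trials | 2.63 | 2.63 | 0.08 |
| Level effect only; 400 trials | −0.08 | −0.08 | −0.07 |
| As first row, 15% of post visits missing at random; 250 trials | 2.70 | 2.70 | 0.14 |

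Monte Carlo SEs are about 0.15, 0.16 and 0.21 by row. In the first row, the unadjusted and listed-model estimates never differed by more than 2 × 10⁻¹⁴ in any trial, and the week 15 level difference moved from 5.29 to 1.46, so visit means are adjusted. In the third row the largest single-trial gap was 0.80 points.

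**Simulation 2.** True difference 15, slope 8, imbalance 0.5 SD, 60 trials. Complete data: 19.2 unadjusted, 19.2 as listed, 14.7 with covariate-by-visit terms (Monte Carlo SE 0.6). With 15% of women losing both post visits: 20.0, 20.0 and 15.3 (SE about 0.7), and single-trial gaps between the first two of up to 2.1 points.

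**Size of the bias.** The documents give neither γ nor δ. Assumed ranges: δ = 0.2 to 0.8 SD and γ = 2 to 8 points per SD, so the bias runs from 0.2 × 2 = 0.4 to 0.8 × 8 = 6.4 points, with a middle case of 0.5 × 5 = 2.5. Actual false-positive rate of the nominal 5% test, using the SEs above:

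| Bias (points) | CCR5 | CD38 |
|---|---|---|
| 0.4 | 5.1% | 5.2% |
| 2.5 | 8.5% | 13.9% |
| 3.0 | 10.1% | 18.0% |
| 6.4 | 28.8% | 60.1% |

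Share of change variance that one covariate would explain: at slope 5, 25/17.4² = 8% (CCR5) and 25/11² = 21% (CD38); at slope 8, 64/11² = 53% (CD38). The top row of the range is therefore a bound, and even the middle case is demanding for CD38.

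**The case against.** - **The plan promises little.** The multivariable paragraph commits only to adjusted means, which main effects do adjust, and section 6.5 speaks only of attempts in an exploratory study. This is fair as to wording. But control of covariates is the only remedy section 6.5 offers for confounding, and the hypotheses are about change.
- **Data will not be complete.** Section 4.1.5 expects some loss to follow-up, section 4.3.1 ends follow-up at pregnancy, and section 5.4 may exclude blood-contaminated specimens. The two results would then be close but not identical. This stands as a limit on exactness. It does not help the model, because the average bias was unchanged with missing visits.
- **The gap is narrow and its size assumed.** Nothing in the documents shows that any of the four covariates is unbalanced or modifies the response. This stands: the defect in the model is certain, but its numerical effect is not. The plan nonetheless names these four as potential confounders.
- **The false-positive rates and simulation 1 use different SEs.** The rates use the plan's 4.49, whereas simulation 1 implies about 3.4 to 3.7. This is correct, and a smaller SE would raise the rates.
- **The time-varying factors are modelled.** Bacterial vaginosis and PSA are handled separately in section 8 and are outside this point.

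**Conclusion.** The point holds. As section 8 lists the model, the four baseline confounders give no adjustment of the between-method difference in pre-to-post change: none at all with complete data, and none on average with the missing-data patterns simulated. This part needs no assumption beyond reading the listed terms as the full model. Its consequence depends on values the documents do not supply. Over the assumed range the bias is 0.4 to 6.4 points against planning differences of 15 and 10, and the middle case of 2.5 points is one-sixth of the CCR5 difference and one-quarter of the CD38 difference. The study is not invalidated, but the correction should be made, because the omission falls on its central comparison and is cheap to repair.

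**What to change.** In the multivariable paragraph of section 8, add the interaction of age, BMI, race and parity with period (pre = weeks 1 and 3; post = weeks 15 and 17). State that the DMPA-minus-Nexplanon and DMPA-minus-Mirena differences in pre-to-post change from that model will be reported with 95% confidence intervals. Keep the week 15 and week 17 contrasts separately available, since section 4.2 plans to "capture data at the trough (week 15) and peak (week 17) of the concentration-time-curve for DMPA".

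The cost is wording, some degrees of freedom and some precision; no new data are needed. With one coefficient per covariate, the period form adds 4 parameters. Interaction with visit also works but adds 4 × 3 = 12 (18 if race is assumed to have four levels), so the period form is leaner. If covariate imbalance inflates the variance of the contrast by an assumed factor of 1.15 or 1.3, CCR5 power falls from 90.7% to 86.5% or 82.1%, and CD38 power from 93.3% to 89.8% or 85.9%. Those figures take no credit for residual variance that the covariates may explain.
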